#### Peri-OP antibiotics

Peri-OP antibiotics at the day before until the day after fistula preparation visits (visit 1c and 4) are allowed if required according to standard of care.

In the event that a patient experiences a disease worsening of CD, as deemed by the investigator, during the course of the trial, the decision whether or not to discontinue treatment and start rescue treatment should be taken in the discretion of the investigator and in discussion with the CTM. Rescue treatment may be any new medication for treatment of CD or any increase in dose of a baseline CD medication.

Stable doses of concomitant therapies for chronic conditions, for which neither the condition nor the treatment are judged to exclude the patient from participation (cf. [Section 3.3](#)) are permissible. All concomitant medications should be carefully evaluated by the investigator and the CTM should be contacted when there are questions regarding concomitant medications.

For further information regarding concomitant therapies and restrictions, see [table 4.2.2.1:1](#).

Details of all concomitant medication will be recorded in the eCRF, along with the main reason for prescription. In addition, all prior treatment for CD at Visit 1a will be recorded including information on reason for discontinuation.

### Management of Adverse Events:

#### Infusion reactions including anaphylactic reaction

- In case of infusion reactions including anaphylactic reaction emerging during or after infusion of trial medication, the investigator should consider in accordance with severity of the reaction and local standard of care to
- Immediately interrupt the infusion
- Treat with systemic anti-histamines, intravenous steroids, and in case of a severe allergic reaction (e.g., anaphylactic reaction) epinephrine

Also draw a plasma sample for IgE and ADA as detailed in the Lab Manual (ISF). Consider also the evaluation of histamine, serum tryptase, and complement components.

In case of infusion reaction, based on patient's clinical course and medical judgment, the infusion may be re-initiated in case of mild or moderate infusion reactions (according to RCTC grading of "allergic reaction / hypersensitivity" in ISF) at lower speed with gradual increase to complete the infusion as detailed in the Instructions for Preparation and Handling of BI 655130/Placebo in the Investigator Site File.

In case of anaphylactic reaction based on the criteria discussed in the statement paper from Sampson HA ([Appendix 10.8 R11-4890](#)) suspected to be caused by the trial medication, the investigator should discontinue treatment with trial medication permanently.

When a non-acute hypersensitivity reaction related to immune complexes (i.e., serum sickness) is suspected, please draw a sample for the laboratory assessment for circulating immune complexes.

#### Severe infections (according to RCTC grading in [Appendix 10.9](#)), serious infections, opportunistic or mycobacterium tuberculosis infections

- Treatment of the infection should be initiated promptly according to local standard of care. No further trial medication should be administered until the active infection has resolved. Treatment with trial medication may be restarted when the patient has recovered according to investigator's assessment.

#### Malignancies

- In case of occurrence of malignant neoplasm other than appropriately treated basal cell carcinoma or squamous cell carcinoma of the skin or in situ carcinoma of uterine cervix, the investigator should discontinue treatment with trial medication. Diagnostics and treatment have to be initiated according to local standard of care.

#### 4.2.2 Restrictions

Section 4.2.2 is applicable for the *Study Cohort* and not for the *Screening Cohort*.

##### 4.2.2.1 Restrictions regarding concomitant treatment

Restrictions regarding previous and concomitant treatment are summarized in table 4.2.2.1: 1

Table 4.2.2.1:1 Restrictions regarding previous and concomitant treatment

Medication or class of medications	Restriction
Any non-biologic medication (incl. cyclosporine, JAK inhibitors such as tofacitinib, tacrolimus, sirolimus, mycophenolate mofetile, S1P modulators, SMAD7 antisense inhibitors such as mongersen), other than those allowed per chapter 4.2.1	Not allowed from 30 days prior to randomisation , unless undetectable plasma concentration, until end of the trial For use as rescue medication, refer to Section 4.2.1 .
Any biologic treatment approved for CD other than anti-TNF <math>\alpha</math> (vedolizumab or ustekinumab)	Not allowed from 8 weeks prior to randomisation, unless undetectable plasma concentration, until end of the trial For use as rescue medication, refer to Section 4.2.1 . Pre-requisites for anti-TNF $\alpha$ treatment, please refer to Section 4.2.1 .

Table 4.2.2.1:1 Restrictions regarding previous and concomitant treatment (cont.)

Any investigational or non-approved biologic for CD (incl. but not limited to IL-23 inhibitors, etrolizumab)
	
Not allowed from 12 weeks prior to randomisation, unless these patients show an undetectable plasma concentration, until end of the trial.
 
Etrolizumab: Not allowed from 8 weeks prior to randomisation, unless undetectable plasma concentration, until end of the trial.
 
For use as rescue medication, refer to Section 4.2.1.

Any immunomodulator allowed per chapter 4.2.1 (azathioprine, 6-mercaptopurine, 6-TG or methotrexate)
	
Only allowed during the trial, if dose is stable for at least 8 weeks prior to randomisation until end of the trial
 
For use as rescue medication, refer to Section 4.2.1.

Autologous or allogeneic, haematopoietic (HSC) or mesenchymal stem cell (MSC) therapy
	
Any prior exposure is not allowed

Faecal Microbiota transplant (FMT)
	
Not allowed from 6 months prior to randomization until the end of the trial

BI 655130
	
Any prior exposure is prohibited


5-ASA
	
Oral administration:
 
Only allowed during the trial, if dose is stable for at least 2 weeks prior to randomisation until end of the trial
 
Rectal route of administration (5-ASA):
 
Not allowed from 2 weeks prior to randomisation up to end of the trial
 
For use as rescue medication, refer to Section 4.2.1.

Table 4.2.2.1:1 Restrictions regarding previous and concomitant treatment (cont.)

Rectal Tacrolimus	Not allowed from 2 weeks prior to randomisation up to end of the trial
Corticosteroids (incl. budesonide)	
Oral administration:          Oral budesonide only allowed at a dose of <math>\leq 9</math> mg per day, and with stable dose for at least 2 weeks prior to randomisation and throughout the trial.          Oral steroids only allowed at a dose of <math>\leq 20</math> mg per day of prednisone or equivalent and with stable dose for at least 2 weeks prior to randomisation and throughout the trial.  Note: Steroids may be reduced after week 12 to a min. dose of 10mg/d (budesonide: 6 mg/d) – see section 4.2.1.
 
Parenteral administration:          Not allowed from 2 weeks prior to randomisation up to end of the trial.  Note: parenteral steroids dosed for less than 24 hours as treatment of infusion or anaphylactic reactions are permitted.
 
Rectal administration:          Not allowed from 2 weeks prior to randomisation up to end of the trial          For use of steroids as rescue medication, refer to Section 4.2.1.

NSAID	
Chronic use not allowed from 2 weeks prior to randomisation up to end of the trial          (Note: occasional use of NSAIDs and acetaminophen for headache, arthritis, myalgias, menstrual cramps, etc., and daily use of baby or low dose (81-162.5mg) aspirin for cardiovascular prophylaxis are permitted.)

Life-attenuated vaccines	Not allowed from 6 weeks prior to randomisation up to end of the trial

Table 4.2.2.1:1 Restrictions regarding previous and concomitant treatment (cont.)

Probiotics (e.g. S. boulardii )	Probiotics only allowed if dose is stable for at least 4 weeks prior to randomization until end of the trial
Antibiotics for IBD	Not allowed from 1 week prior to randomisation up to end of the trial. Peri-OP antibiotics at the day before until the day after fistula preparation visits (visit 1c and 4) are allowed if required according to standard of care.
Anti-diarrheals	No restrictions

#### 4.2.2.2 Restricted fistula interventions

Surgical interventions for CD are not allowed during the trial.

Any surgical intervention or procedure for perianal and enterocutaneous fistulas (except seton drainage) are also not allowed ( patient shall be discontinued) since they would interfere with the clinical endpoints of the trial. These are summarized in table 4.2.2.2:1. ( no exhaustive list).

Table 4.2.2.2:1 Restrictions regarding procedures for perianal and enterocutaneous fistulas

Procedure for perianal and enterocutaneous fistulas	Restriction
- Cutting of fistulas - Shortening of fistulas - Splitting of fistulas - Fibrin glue	Not allowed from start of screening (screening visit 1a) until end of the trial

#### 4.2.2.3 Restrictions on diet and life style

No specific restrictions on diet or life style of the patients are required.

#### 4.2.2.4 Restrictions regarding women of childbearing potential

Female patients of child bearing potential must maintain adequate contraception throughout the course of the trial and up to 16 weeks after the last study drug administration.

Women of childbearing potential must use highly effective contraception methods described below:

- Combined (estrogen and progestogen containing) hormonal birth control associated with inhibition of ovulation.
- Progestogen-only hormonal birth control associated with inhibition of ovulation.
- Intrauterine device (IUD) and intrauterine hormone-releasing system (IUS).
- Bilateral Tubal occlusion (blocking of the fallopian tubes).

- Vasectomy of sexual partner (proven effective by absence of sperm on the ejaculation).
- Complete sexual abstinence (not to have male-female vaginal sex)\*.

\*Refraining from heterosexual intercourse during the entire trial. The reliability of sexual abstinence needs to be evaluated in relation to the duration of the clinical trial and the preferred and usual lifestyle of the patient

As monoclonal antibodies can be secreted in milk, women should refrain from breastfeeding once they receive the study drug and up to 16 weeks after, i.e. until BI 655130 is eliminated. They can start nursing again after this period.

### **4.3 TREATMENT COMPLIANCE**

Study medication will be administered in accordance with the protocol by authorised study personnel (e.g. study nurse).

[REDACTED]

Any missed dose has to be documented and reported to the CTM.

## 5. ASSESSMENTS

### 5.1 ASSESSMENT OF EFFICACY

#### 5.1.1 Screening Cohort

#### 5.1.2 Study Cohort

##### Perianal fistula activity

The Perianal fistula activity will be evaluated using the following definitions:

- *Perianal fistula remission*  
A *perianal* fistula remission is defined as closure of all external openings, no drainage / discharge despite gentle finger compression of fistulas, that were draining at baseline and without new emerging fistulas as assessed by physical examination by investigator(s) on site
- *Perianal fistula response*  
A *perianal* fistula response is defined as closure at least 50% of external openings, no drainage / discharge despite gentle finger compression of fistulas, that were draining at baseline and without new emerging fistulas as assessed by physical examination by investigator(s) on site
- *Combined perianal fistula remission:*  
The achievement of *combined perianal* fistula remission drives the decision for treatment allocation at the start of period 2.  
A *combined perianal* fistula remission is defined as closure of all external openings, no drainage / discharge despite gentle finger compression of fistulas, that were draining at baseline and without new emerging fistulas, AND absence of collections >2 cm, confirmed by MRI in at least two of three dimensions – blinded and centrally read.  
The treatment allocation decision from Week 12 onwards is based on physical examination performed by investigator(s) on site and MRI reading (no central reading needed for treatment allocation decision at week 12, central reading will be mandatory only for efficacy assessment purposes) .

##### Fistula Preparation Visit (FPV)

The FPV with examination of anus and rectum using the endoscope as well as examination and drainage of fistula via curettage (if required) may need to be done in anesthesia or narcosis at the investigator`s discretion according to local standard of care.

Tissue will be taken from all perianal fistulas drained by a seton placed at visit 1c (cf. [section 3.1](#)).

[REDACTED]

[REDACTED]

[REDACTED]

[REDACTED]

[REDACTED]

[REDACTED]

## 5.2 ASSESSMENT OF SAFETY

Safety will be assessed descriptively based on:

- Physical examination
- Vital signs
- Clinical laboratory values (haematology, clinical chemistry, coagulation and urinalysis), not applicable for Screening Cohort
- 12-lead ECG, not applicable for Screening Cohort
- Adverse events
- Serious adverse events (SAEs)
- Intensity of adverse events will be assessed by Rheumatology Common Toxicity Criteria (RCTC) version 2.0 (refer to ISF for details)

### 5.2.1 Physical examination

A *complete physical examination* will be performed at the time points specified in the flowchart. It includes vital sign assessment and general appearance as well as evaluation of all organ systems.

*Targeted physical examination* will include vital sign assessment and evaluation of organ systems associated with AE(s) symptoms or laboratory abnormalities.

Measurement of height and body weight will be performed at the time points specified in the flowchart.

Clinically relevant abnormal findings will be reported as baseline conditions or AEs.

### 5.2.2 Vital signs

Vital signs evaluations will be performed at visits as shown in the [Flow Chart](#), prior to blood sampling.

This includes temperature, pulse rate (electronically or by palpation count for 1 minute), systolic/diastolic blood pressure and respiratory rate in a seated position after at least 5 minutes of rest.

#### Study Cohort:

At dosing visits vital signs evaluations will be performed *pre-dose* and additional evaluation will be taken at approximately *10 minutes and 1 hour post-dose*.

Monitoring for hypersensitivity reactions:

Patients should be closely monitored for signs and symptoms of hypersensitivity reactions for approximately *2 hours* after the *first dose* administered at visit 2 and *1 hour* following all *other doses* of study drug. Hypersensitivity reactions should be treated according to medical standards. Pre-medications for further infusions might be considered and will be agreed on between investigator and BI clinical monitor.

The investigator should evaluate the clinical significance of the results. Clinically abnormal findings will be reported as baseline condition or AEs.

### 5.2.3 Safety laboratory parameters

The safety laboratory samples will be taken for the *Screening Cohort* according to their local standard of care. No specific parameters are requested.

[Section 5.2.3](#) is applicable for the *Study Cohort*, only.

Safety laboratory parameters to be assessed are listed in [Table 5.2.3:1](#) and [5.2.3:2](#). For the sampling time points please see the [Flow Chart](#). More frequent blood sampling may be done whenever the investigator deems necessary. Unscheduled safety laboratory examinations will be reported in the CRF along with the results.

All safety laboratory analyses will be performed by a local laboratory.

It is preferred but the patients do not have to be fasted for the blood sampling for the safety laboratory.

It is the responsibility of the investigator to evaluate the laboratory results from the local laboratory.

Clinically relevant abnormal findings as judged by the investigator will be reported as baseline conditions or adverse events (please refer to [Section 5.2.6](#)).

A clinically relevant value may be either in- or outside the reference range. Clinically relevant abnormal laboratory test results must be confirmed and should be repeated until normalization or stabilization or until an alternative explanation has been found. Abnormal laboratory values will be also graded for intensity by using RCTC Version 2.0 criteria. ([R13-3515](#)).

In case the criteria for hepatic injury are fulfilled, a number of additional measures will be performed (please see [Section 5.2.6.1](#)) and the DILI Checklist provided in the ISF eDC system. The amount of blood taken from the patient concerned will be increased due to this additional sampling.

Table 5.2.3: 1 Exclusionary testing

Category	Test name
Infection testing	Hepatitis B Surface Antigen (qualitative)  Hepatitis B core Antibody  HBV-DNA (quantitative PCR)  Hepatitis C Antibodies (qualitative)  HIV-1, and HIV-2 Antibody (qualitative) 
TB screening	QuantiFERON®-TB 
Serum Pregnancy test (only for female patients of childbearing potential) 1)	Human Serum Chorionic Gonadotropin
Stool studies to evaluate for enteric pathogens 1)	Salmonella Shigella Yersinia Campylobacter E. coli Clostridia difficile toxin Enteric parasites and their ova (including Cryptosporidia)

 At screening only (visit 1)

 A HBV-DNA should be conducted if Hepatitis B core Antibody is positive and Hepatitis B Surface Antigen is negative (definition of occult HBV infection: B core Antibody is positive, Hepatitis B Surface Antigen is negative; HBV DNA detectable).

 There is the trial site option to perform a PPD skin test

 If the 1st QuantiFERON®-TB test result is undetermined, a re-test should be performed. If the re-test QuantiFERON-TB test result is undetermined, a PPD skin test should be performed.

Table 5.2.3: 2 Laboratory tests

Category	Test name
Haematology	Haematocrit (Hct) Haemoglobin (Hb) Glycosylated Hbc (HbA1c) (only at screening) Red Blood Cell Count/ Erythrocytes Reticulocyte Count White Blood Cells / Leukocytes Platelet Count/ Thrombocytes
Diff. Automatic	Neutrophils (relative and absolute count) Eosinophils (relative and absolute count) Basophils (relative and absolute count) Monocytes (relative and absolute count) Lymphocytes (relative and absolute count)
Diff. Manual (if Diff Automatic is abnormal)	Neutrophils, bands (Stabs) Neutrophils, polymorphonuclear (PMN) Eosinophils Basophils Monocytes Lymphocytes
Coagulation	Activated Partial Thromboplastin Time (aPTT) Prothrombin time (INR) Fibrinogen
Enzymes	AST (GOT) ALT (GPT) Alkaline Phosphatase (AP) Creatine Kinase (CK) CK-MB, only if CK is elevated Gamma-Glutamyl Transferase (GGT/ $\gamma$ -GT) Lactic Dehydrogenase (LDH) Amylase Lipase
Electrolytes	Calcium Sodium Potassium Chloride
Substrates	Glucose BUN (blood urea nitrogen) Uric acid Creatinine eGFR (estimated by CKD-EPI formula) (only at screening) Bilirubin Total Bilirubin Direct (if total is elevated) Bilirubin Indirect (if total is elevated) Troponin (Reflex, in case of elevated CK) Protein, Total Albumin C-Reactive Protein (CRP) Cholesterol, total Triglycerides LDL-Cholesterol HDL-Cholesterol

Table 5.2.3: 2 Laboratory tests (cont.)

Category	Test name
Specific gamma-globulin quantification	IgE  , IgG
Urine Pregnancy test (only for female patients of childbearing potential)	Human Chorionic Gonadotropin in urine
Serum Pregnancy test (only for female patients of childbearing potential if urine pregnancy test is positive)	Human Serum Chorionic Gonadotropin
Hormones (only at screening)	TSH (free T3 and free T4 in case of abnormal TSH result)
Urinalysis (dipstick)	Urine Nitrite Urine Protein Urine Glucose Urine Ketone Urobilinogen Urine Bilirubin Urine RBC/ Erythrocytes Urine WBC/ Leukocytes Urine pH
Urine-Sediment (microscopic examination, only if urine analysis abnormal)	Urine Sediment Bacteria Urine Cast in Sediment Urine Squamous Epithelial Cells Urine Sed. Crys., Unspecified Urine Sediment RBC/ Erythrocytes Urine Sediment WBC/ Leucocytes
Urine (only at screening)	Albumin (quantitative)
Infections screening	HBV-DNA (quantitative) at EOT Visit 
QuantiFERON-TB test	QuantiFERON®-TB at EOT visit 

Only in case of allergic reaction

HBV-DNA in case of occult HBV infection (for definition see [Table 5.2.3: 1](#) footnote 2)

 There is the trial site option to perform a PPD skin test

 If the 1st QuantiFERON®-TB test result is undetermined, a re-test should be performed. If the QuantiFERON-TB re-test result is undetermined, a PPD skin test should be performed.

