## FLOW CHART B: STUDY COHORT, PERIOD 1 (SCREENING – WEEK 8)

Trial Periods	Screening Period*			Randomized Treatment Period			
	Visit	V1a (Screening)	V1b (Pre-baseline)	V1c	V2 (Base-line)	V3	V4
Week	-5 to -3	-5 to -3	-3	0	2	4	8
Day	-35 to -22	-35 to -21	-21	1	15	29	57
Time window for visits (days)	n.a.	n.a.	+ 4	n.a.	± 4	± 4	± 4
Informed consent	X						
In-/exclusion criteria	X		X				
Demographics	X						
Medical history incl. smoking, Crohn's Disease history	X						
Prior therapies	X						
Physical examination (incl. vital signs) 1)	X C			X T	X T	X T	X T
Weight, Height 15)	X			X		X	X
Pregnancy Test 2)	X			X		X	X
[REDACTED]							
[REDACTED]			X			X	
Fistula preparation visit: 4) Biopsy at the inner fistula orifice Curettage at the fistula canal [REDACTED]			X			X	
Seton placement			X				
Seton removal						X	
[REDACTED]			X			X	
[REDACTED]			X Before Surgical Procedure			X	
[REDACTED]	D		X R Before Surgical Procedure	D	XR D	XR D	XR D
Imaging Pelvic MRI [REDACTED]			X  Before Surgical Procedure at V1c				
Concomitant therapy	X			X	X	X	X
Adverse events	X	X	X	X	X	X	X
12 lead-ECG	X			X			
Safety laboratory tests 6)	X			X	X	X	X
Infection testing 7)	X						

Flow Chart B: STUDY Cohort, Period 1 (Screening – Week 8) (cont.)

Trial Periods	Screening Period*			Randomized Treatment Period			
	V1a (Screening)	V1b (Pre-baseline)	V1c	V2 (Base-line)	V3	V4	V5
Week	-5 to -3	-5 to -3	-3	0	2	4	8
Day	-35 to -22	-35 to -21	-21	1	15	29	57
Time window for visits (days)	n.a.	n.a.	+ 4	n.a.	± 4	± 4	± 4
QuantIFERON-TB test	X						
[REDACTED]				■	■	■	■
[REDACTED]				X	X	X	X
[REDACTED]				X		X	X
[REDACTED]				■			
[REDACTED]				■		■	■
[REDACTED]				■		■	
[REDACTED]	X						
[REDACTED]				X			X
Contact IRT	X			X		X	X
Randomization				X			
Study drug administration				X 12,13		X 13, 14	X 13

\*) Once the gene expression analyses from the obtained fistula canal samples in the SCREENING COHORT have confirmed the eligibility criteria, enrolment of the STUDY COHORT will be initiated. Otherwise, the sponsor may decide to amend the study in order to obtain the relevant tissue from all study participants.

1) Physical examination: C=complete, T=targeted. Refer to [Section 5.2.1](#).

Vital signs: Measurement should precede blood sampling to avoid the impact of blood sampling on the vital measurements. In addition, at dosing visits vital signs will be assessed pre-dose, approximately 10 minutes and 1 hour after study drug administration.

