Treatment assignment in period 2 will be determined by the achievement of combined perianal fistula remission at week 12 based on assessment by investigator(s) on site.

- Combined perianal fistula remission = yes: stay on current drug
- Combined perianal fistula remission = no: switch to active drug if treated with placebo in period 1  
 proceed with active drug if treated with active drug already in period 1

5) MRI

Visit 6:

MRI to be performed in a time window of 2 weeks PRIOR to visit 6. MRI result to be available at visit 6 for the evaluation of combined perianal fistula remission performed by investigator(s) on site.

6) Includes parameters as listed in [Table 5.2.3:1](#) and [5.2.3:2](#).

It is preferred but patients do not have to be fasted for the blood sampling for the safety laboratory. At visits with study drug administration this should be done prior to the study drug infusion.

[REDACTED]

10) Patients who terminate study drug early should be encouraged to follow all study procedures per the [Flow Chart](#) until week 24, but not receive any more study drug at the respective visits. These patients do have the option to do EOS visit earlier than week 36 (their EOS visit should not be earlier than 16 weeks after their last study drug administration). Until then they should follow the Flow Chart.

11) Visit 6: I.v. administration and related procedures may be done within max. of 3 days after other investigations / procedures, if otherwise too difficult due to logistical reason

12) All patients completing week 24 of the study and having an individual clinical benefit may be offered to enter open label long-term extension study 1368-0007. These patients are not requested to complete follow up period and the visit 09 is the last visit for trial 1368-0008, probably co-inciding with the first visit in 1368-0007. For AE and Concomitant therapy reporting the end of study participation is defined as the day of first administration of study drug in 1368-0007.

[REDACTED]

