#### 3.3.3.2.2 Infectious Disease Exclusion Criteria

11. Increased risk of infectious complications (e.g. due to past organ or stem cell transplantation)
12. Live or attenuated vaccination within 6 weeks prior to randomization
13. Patients with a positive QuantiFERON TB test during screening are excluded, unless:
  - Patient had previous diagnosis of active or latent TB and has completed appropriate treatment per local practice/guidelines within the last 3 years and at least 6 months before first administration of trial medication under this protocol (patients may be re-screened once to meet this criterion)
  - Patients with suspected false positive or indeterminate QuantiFERON TB result may be re-tested once
  - If Quantiferon not available or providing indeterminate results after repeat testing : A tuberculin skin test reaction  $\geq 10\text{mm}$  ( $\geq 5\text{mm}$  if receiving  $\geq 15\text{mg/d}$  prednisone or its equivalent)
14. Relevant chronic or acute infections including active tuberculosis, human immunodeficiency virus (HIV) infection or viral hepatitis. A patient can be re-screened if the patient was treated and is cured from the acute infection.

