Description of change		Screening of patients for Study Cohort may stay open until approximately 15 patients have valid baseline and post treatment biopsies for primary endpoint analysis.
Rationale for change		Minimum of approx. 15 patients may be needed for primary endpoint analysis.
Section to be changed		Section 3.3.4.1
Description of change		Add the following bullet point for discontinuation from trial treatment: The investigator clinical judgement advises for it.
Rationale for change		Clarify that based on the judgement of the investigator, patients may be discontinued from trial treatment.
Section to be changed		Section 4.2.1
Description of change		Updated wording of steroid tapering in order to

		allow steroid tapering schedule according to standard of care.
Rationale for change		Give more flexibility to investigators for steroid tapering
Section to be changed		Sections 4.2.1, 4.2.2
Description of change		Peri-OP antibiotics at the day of the fistula preparation visits (visit 1c and 4) are allowed if required according to standard of care.
Rationale for change		Clarification in respective chapters (already described in figure 3.1:1)
Section to be changed		Section 5.2.3
Description of change		Clarification in table 5.2.3:1 (exclusionary testing) and 5.2.3:2 (removal of calprotectin from local safety laboratory)
Rationale for change		Clarification exclusionary testing: HBV-DNA and QuantiFERON®-TB will be repeated at EOT; Calprotectin will be analysed by central laboratory, no additional testing by local laboratory necessary
Section to be changed		Section 5.2.6.2
Description of change		AE reporting: Distinguish between patients who roll-over to maintenance trial 1368-0007 and who not roll-over. Patients who roll-over to 1368-0007 AE reporting will be done from signing the informed consent (1368-0008) onwards until the first dose of trial medication in 1368-0007.
Rationale for change		Harmonization of AE reporting with trial 1368-0007.
Section to be changed		Appendix 10.4
Description of change		Add weighting to [REDACTED]
Rationale for change		Clarification
Section to be changed		Several chapters
Description of change		Minor editorial changes were done across the protocol
Rationale for change		Clarification

11.2 GLOBAL AMENDMENT 2

Date of amendment		02 Apr 2020

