Description of change		Amended definition for "individuals patients end", "end of the trial" and clarification on AE/CT reporting timeline for patients who roll-over to 1368-0007.
Rationale for change		Clarification
Section to be changed		Flow Chart C
Description of change		Removal of infection testing for EOT visit in Flow Chart C
Rationale for change		Correction, in order to harmonize the Flow Chart C with table 5.2.3:1 which states that infection testing is required for screening, only.
Section to be changed		Section 5.3.2
Description of change		
Rationale for change		Correction to align with Laboratory Manual.
Section to be changed		Section 6.2.2.3
Description of change		Amended wording for patients who roll-over to 1368-0007 (patient information).
Rationale for change		Clarification, avoid inconsistencies with CTP 1368-0007
Section to be changed		Section 7.3
Description of change		The FAS will follow the intent-to-treat principle and the handling of patients who received a wrong treatment will be described in the TSAP.
Rationale for change		Added additional information for clarification
Section to be changed		Several chapters
Description of change		Minor editorial changes were done across the protocol

Rationale for change		Clarification
Section to be changed		4.2.1
Description of change		Peri-OP antibiotics at the day before until the day after fistula preparation visits (visit 1c and 4) are allowed if required according to standard of care.
Rationale for change		Allow more flexibility in order to address local standard of care

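### The end-of-treatment HBV-DNA test is tied to a definition that requires detectable DNA, so it misses the core-antibody-positive patients who can be enrolled

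*Protocol*

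**What the plan says.** Protocol section 5.2.3 contains two conditional rules for HBV-DNA.

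- **Screening (Table 5.2.3:1, footnote 2).** "A HBV-DNA should be conducted if Hepatitis B core Antibody is positive and Hepatitis B Surface Antigen is negative". The condition is serological; no DNA result is needed to trigger the test.
- **EOT, Visit 9 (Table 5.2.3:2, footnote 2).** "HBV-DNA in case of occult HBV infection". For the meaning of the term, this footnote refers back to Table 5.2.3:1 footnote 2, which gives a "definition of occult HBV infection: B core Antibody is positive, Hepatitis B Surface Antigen is negative; HBV DNA detectable".

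Table 5.2.3:1 is titled as exclusionary testing. Exclusion criterion 14 (section 3.3.3.2.2) rules out "Relevant chronic or acute infections including active tuberculosis, human immunodeficiency virus (HIV) infection or viral hepatitis". No criterion mentions core-antibody status or an HBV-DNA result by name.

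On scheduling, Flow Chart B has a row "Infection testing 7" marked at Visit 1a only, and Flow Chart C has no such row. Footnote 6 of both charts says of the safety laboratory tests: "Includes parameters as listed in" Tables 5.2.3:1 and 5.2.3:2.

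**The concern.** The two triggers differ by one element, detectable DNA, and that element changes whom the EOT test reaches. Under the EOT rule a patient must already have had detectable DNA, yet such a patient would normally have been screened out. The patients for whom a later test could give new information are those with positive core antibody, negative surface antigen and no detectable DNA at entry. They can be enrolled, and the rule leaves them out.

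HBV reactivation is named among the opportunistic infections that count as adverse events of special interest (section 5.2.6.1), and patients may stay on immunosuppressants or anti-TNF agents (section 4.2.1). For opportunistic infections, section 4.2.1 requires prompt treatment and withholding of study drug until resolution, which works only if the infection is detected. For patients who roll over, Visit 9 is the last visit of this trial before up to 7 further years of BI 655130 (section 3.2).

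**Working it through.** The plan states no figure to reproduce. The check sets each HBV marker pattern against the eligibility rules and the two triggers.

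| Pattern at screening | Eligible? | HBV-DNA at screening? | HBV-DNA at EOT? |
|---|---|---|---|
| (a) Surface antigen positive | Normally excluded (criterion 14) | No | No, not occult |
| (b) Surface antigen negative, core antibody positive, DNA detectable | Normally excluded (exclusionary table, criterion 14) | Yes | Yes |
| (c) Surface antigen negative, core antibody positive, DNA undetectable | No named criterion excludes | Yes | No, not occult |
| (d) Surface antigen negative, core antibody negative | Not excluded on HBV grounds | No | No |

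Only pattern (b) triggers the EOT test, and (b) is a pattern the screening tests appear designed to exclude. Pattern (c) had HBV-DNA ordered at screening, can be enrolled, and drops out of the EOT rule.

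**Does another rule schedule the test for (c)?** Footnote 6 of the flow charts brings Table 5.2.3:1 into the safety laboratory, and HBV-DNA is the one infection test in that table without the screening-only mark. This leaves some ambiguity. Against it, Flow Chart B marks infection testing at Visit 1a only. The rationale in Global Amendment 3 (section 11.3) describes Table 5.2.3:1 as one "which states that infection testing is required for screening, only". If HBV-DNA already ran at every safety laboratory visit on the wider trigger, the separate and narrower EOT entry would also be redundant. For intent only, the rationale in Global Amendment 1 (section 11.1) says that HBV-DNA "will be repeated at EOT". A repeat fits patients who were tested at screening and then enrolled, which is pattern (c).

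**Scheduled tests for a pattern (c) patient**

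- Clearly scheduled HBV-DNA tests after screening: 0.
- Safety laboratory visits after the first dose, all including ALT, AST and bilirubin: V3, V4, V5 (Flow Chart B) plus V6 to V10 (Flow Chart C) = 3 + 5 = 8. Up to EOT (V9): 8 − 1 = 7.
- Interval from the Visit 1a test (week −5 to −3) to EOT (week 24): 24 + 3 = 27 weeks to 24 + 5 = 29 weeks.

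**Number of patients.** The documents give no prevalence for pattern (c). Assuming 1% to 10%, and that all such patients pass the discretionary criteria, the expected number among about 20 randomised is 20 × 0.01 = 0.2 to 20 × 0.10 = 2.

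**The case against.** The strongest counter-argument is the footnote 6 reading: HBV-DNA alone lacks the screening-only mark, so pattern (c) patients could be tested whenever safety blood is drawn, Visit 9 included. The missing infection-testing row in Flow Chart C proves little, because the EOT test that Table 5.2.3:2 does list has no row of its own there either. An amendment rationale is not operative text. This stands as a real ambiguity, and it is why the claim is limited to no clearly scheduled retest. It does not remove the mismatch, because the only entry written specifically for EOT still carries the narrower condition.

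Second, criterion 14 excludes relevant infections and does not say what a detectable HBV-DNA result means. An investigator might judge an occult infection not relevant and enrol the patient, so the EOT trigger may have some population. That also stands, and the claim is therefore few or no patients. Pattern (c) is missed either way.

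Third, other safeguards exist: liver enzymes and bilirubin at every safety laboratory visit, the hepatic-injury procedure, and extra samples or unscheduled visits at the investigator's discretion. These would find many reactivations. However, the defined alert requires ALT or AST at least 3 × ULN together with bilirubin at least 2 × ULN, or ALT or AST at least 10 × ULN (section 5.2.6.1). Smaller changes rest on judgement, and reactivation without enzyme changes has no clearly scheduled test.

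Fourth, the number of patients is small and unknown, and how much reactivation risk pattern (c) carries is a clinical question the documents do not answer. Both points limit the weight of the finding, as does the fact that the extension study's own testing is not described here.

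**Conclusion.** The concern holds. Followed as written, the EOT HBV-DNA test falls on few or no correctly enrolled patients, and the enrollable patients whose serology prompted the screening test have no clearly scheduled retest over about 27 to 29 weeks. This rests on two readings: that detectable DNA normally leads to exclusion under criterion 14, and that Table 5.2.3:1 infection testing applies at screening only. Both are the better reading of the text, but neither is stated outright.

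The practical effect is limited. It concerns perhaps 0.2 to 2 of about 20 patients under an assumed prevalence, and liver-enzyme monitoring partly covers it. No primary or secondary endpoint analysis is affected. It should still be corrected, because a safety test the sponsor chose to include misses its likely target and the correction costs very little.

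**What to change.** Replace the condition in Table 5.2.3:2 footnote 2 with the serological trigger already used at screening, for example: *HBV-DNA at EOT if Hepatitis B core Antibody was positive and Hepatitis B Surface Antigen negative at screening.* The planned test then reaches the intended patients before follow-up or roll-over.

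The cost is one footnote by amendment and one extra run of an assay already in the plan, in the few core-antibody-positive patients, at a visit where safety blood is drawn anyway. A single test at week 24 does not detect reactivation in real time during dosing. Whether to add on-treatment tests, and how to manage a positive result, are decisions for the clinical team.
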